6.6.4.1. Within-Day Variability

For variables assessing within-day variability, first determine the variability within each valid CGM day, then average across days within a CGM session.

Within-day glucose SD (Rodbard 2009):

$$SD = \frac{1}{m} \sum_{k=1}^m SD_k = \frac{1}{m} \sum_{k=1}^m \sqrt{\frac{\sum_{i=1}^n (BG_{k,i} - \left\{ \frac{\sum_{i=1}^n BG_{k,i}}{n} \right\})^2}{n-1}}$$

Within-day glucose CV (Clarke and Kovatchev 2009):

$$CV = \frac{1}{m} \sum_{k=1}^m CV_k = \frac{1}{m} \sum_{k=1}^m \frac{SD_k}{\left(\frac{\sum_{i=1}^n BG_{k,i}}{n} \right)} \times 100$$

The low blood glucose index (LBGI), high blood glucose index (HBGI), and blood glucose risk index (BGRI) will be calculated using the following standard formulas (Kovatchev et al. 2006).

The LBGI, HBGI, and BGRI will be derived for each valid CGM day of a visit and then average across days within a CGM session. The calculations of LBGI, HBGI and BGRI take the following steps:

1. For each blood glucose (BG [mg/dL]) at the i^{th} time point, compute the following:

$$f(BG_i) = 1.509 \times [(\ln(BG_i))^{1.084} - 5.381]$$

2. Compute BG risk for each reading

$$\begin{aligned} rl(BG_i) &= 10 \times f(BG_i), \text{ if } f(BG_i) < 0; \text{ otherwise } rl(BG_i) = 0 \\ rh(BG_i) &= 10 \times f(BG_i), \text{ if } f(BG_i) > 0; \text{ otherwise } rh(BG_i) = 0 \end{aligned}$$

3. Compute LBGI and HBGI

$$LBGI = \frac{1}{n} \sum_{i=1}^n rl(BG_i)$$

$$HBGI = \frac{1}{n} \sum_{i=1}^n rh(BG_i)$$

4. Compute BGRI

$$BGRI = LBGI + HBGI$$

6.6.4.2. Between-Day Variability

For variables assessing between-day variability, first determine the variability for each time point across days within a CGM session then average across all time points.

Between-day glucose SD (Rodbard 2009):

$$SD = \frac{1}{n} \sum_{i=1}^n SD_i = \frac{1}{n} \sum_{i=1}^n \sqrt{\frac{\sum_{k=1}^m (BG_{k,i} - \left\{ \frac{\sum_{k=1}^m BG_{k,i}}{m} \right\})^2}{m-1}}$$

Between-day glucose CV (Kovatchev et al. 2009):

$$CV = \frac{1}{n} \sum_{i=1}^n CV_i = \frac{1}{n} \sum_{i=1}^n \left(\frac{SD_i}{\left(\frac{\sum_{k=1}^m BG_{k,i}}{m} \right)} \right) \times 100$$

Mean of daily differences (MODD): this parameter is calculated as the mean of absolute differences between glucose values at corresponding time points of consecutive days.

$$MODD = \frac{1}{m-1} \sum_{k=1}^{m-1} \frac{\sum_{i=1}^n |BG_{k+1,i} - BG_{k,i}|}{n}$$

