6.6. Appendix 6: Derivation of CGM Variables

Blinded CGM will be worn by participants at the following designated weeks:

- Two weeks in screening/lead-in period with the data download at Visit 3 (Week 0),
- Four weeks after the initiation of study treatment with the data download at Visit 7 (Week 4),
- Four weeks from V7 (Week 4) with the data download at Visit 11 (Week 8) (only for sites in Japan),
- Four weeks near the end of weekly titration period with the data download at Visit 15 (Week 12),
- Four weeks near the end of half year treatment with the data download at Visit 24 (Week 26),
- Four weeks near the primary endpoint with the data download at Visit 31 (Week 52), and
- Four weeks after the end of study treatment period with the data download at Visit 802 (Week 57).

Dexcom G6 system will be used in all countries to collect CGM data except China. In China, Libre Freestyle H system will be used instead.

Linear interpolation will be used to impute the missing glucose readings during intervals >7 minutes and ≤ 15 minutes. Missing data will be imputed at a 5-minute interval using the BG value before and the one after the interval.

For example, the BG reading before the interval is 50 mg/dL at time 100 min, and the BG reading after interval is 70 at time 115 min, then the missing records will be imputed as:

- at time 105 min, BG reading= $50+5*(70-50)/(115-100)=56.7$, and
- at time 110 min, BG reading= $50+10*(70-50)/(115-100)=63.3$.

Glucose reading intervals >15 minutes will be treated as missing data and not be counted in the length of the analysis periods. Since the Libre Freestyle H system normally provides readings every 15 minutes, the linear interpolation missing data imputation will not be performed.

As shown in the table below, all the CGM derivations are based on the data from valid CGM periods of a day and sessions unless otherwise specified.

Minimum Data Available to Define a Valid Period of the Day and CGM Session

Period	Definition of Valid Period	Definition of Valid CGM Session
Valid CGM Day (00:00-23:59)	$\geq 70\%$ of expected values available (≥ 202 of 288 values for Dexcom G6 system; ≥ 68 of 96 values for Libre Freestyle H system)	≥ 3 valid CGM days within a visit define a valid CGM visit. A valid CGM session only includes valid CGM visits.

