6.6.4. Glycemic Variability

Glycemic variability will be derived using the notation below:

- i represents a time point within a time period (a 24-hour period, daytime or nighttime);
- n represents the number of time points within the time period;
- k represents a valid CGM day within a visit;
- m represents the number of valid CGM days in the specific time period at a visit; and
- $\text{BG}_{k,i}$ represents the glucose value at time point i on day k unless otherwise specified.

Sections 6.6.4.1 and 6.6.4.2 provide the derivation method for variables assessing within-day and between-day glucose variability based on CGM readings.

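### The MODD formula averages over successive valid CGM days, which need not be the consecutive days of its own definition when an invalid day falls between valid ones

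*SAP*

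**What the plan says.** SAP 6.6.4.2 describes MODD this way: "this parameter is calculated as the mean of absolute differences between glucose values at corresponding time points of consecutive days". The formula sums the absolute difference between day k+1 and day k at each time point i, divides by n within each pair of days, and averages over k = 1 to m-1.

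The indices are defined in SAP 6.6.4: "k represents a valid CGM day within a visit" and "m represents the number of valid CGM days in the specific time period at a visit". SAP 6.6 sets validity. A day needs at least 70% of its expected readings (at least "202 of 288 values for Dexcom G6 system"). A minimum of three "valid CGM days within a visit define a valid CGM visit", with no requirement that they be adjacent. "A valid CGM session only includes valid CGM visits".

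No date condition on the pairs appears in Appendix 6. The unit also varies: SAP 6.6.4 counts days at a visit, while the opening sentence of 6.6.4.2 works across days within a CGM session.

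Glucose variability in the sessions before Weeks 26 and 52 is listed under other secondary endpoints in SAP 1.1. SAP 2.1 makes no multiplicity adjustment for that tier.

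**The concern.** The words and the formula describe different quantities once a day inside the recording is invalid. Day k+1 is then the next valid day, not the next date. A programmer following the sentence and one following the notation would get different values from the same record, and nothing in the SAP says which governs.

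Invalid days are to be expected: the plan has a completeness rule for days, and Protocol 8.1.1.2 sets an 80% session threshold for re-education. Under the formula, MODD depends partly on the pattern of wear as well as on glucose. If that pattern, or the way glucose changes from day to day, differs between a weekly and a daily insulin, part of an observed difference in MODD could come from the derivation.

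**Working it through.** The SAP states no MODD value, so there is no figure to reproduce. The check reads the formula literally and then sizes the effect under stated assumptions.

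**Inputs from the SAP.** The formula (6.6.4.2), the meaning of k and m (6.6.4), and the four-week session, or 28 days (6.6). **Assumed, because the documents do not give them:** the correlation between adjacent days, and the number and placement of invalid days.

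**1. Literal reading.** Let days 1, 2 and 4 be valid. Then m = 3 and the formula averages m-1 = 2 pairs, days 1-2 and days 2-4. Only the first is consecutive.

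**2. Single records can move either way.** Take one value per day on days 1, 2 and 4.
- Values 100, 120, 130: the formula gives (20 + 10)/2 = 15; the adjacent pair alone gives 20.
- Values 100, 120, 170: the formula gives (20 + 50)/2 = 35; the adjacent pair alone gives 20.

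**3. Expected effect.** For stationary Gaussian values with correlation ρ^g at a gap of g days, the expected absolute difference relative to adjacent days is R(g) = √[(1 − ρ^g)/(1 − ρ)]. For g = 2 this is √(1 + ρ). The session ratio (formula over adjacent pairs only) is 1 + (share of pairs affected) × (R − 1).
- One isolated interior invalid day in 28: m = 27, 26 pairs, 1 affected. At ρ = 0.5: 1 + (1.225 − 1)/26 = 1.009.
- Eight isolated interior invalid days: m = 20, 19 pairs, 8 affected. At ρ = 0.5: 1 + 8 × (1.225 − 1)/19 = 1.095.

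| Assumed ρ | R(2) | One gap | Eight gaps |
|---|---|---|---|
| −0.3 | 0.837 | 0.994 | 0.931 |
| 0 | 1.000 | 1.000 | 1.000 |
| 0.2 | 1.095 | 1.004 | 1.040 |
| 0.5 | 1.225 | 1.009 | 1.095 |
| 0.7 | 1.304 | 1.012 | 1.128 |

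**4. Simulated 28-day sessions, days invalid at random.**
- 10% invalid: ratio 0.984 (ρ = −0.3), 1.000 (0), 1.010 (0.2), 1.024 (0.5).
- 30% invalid: 0.955, 0.999, 1.031 and 1.077 for the same correlations.
- Invalid days only at the start and end of the session, ρ = 0.5: 1.000.
- A separate simulation with added within-day noise (daily-level SD 20 mg/dL, noise SD 18), ρ of 0.3 to 0.8, an optional 7-day cycle and 10% to 30% of days invalid gave 1.005 to 1.046.

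**5. Time points.** Two valid Dexcom days may each have only 202 of 288 readings. They can then share as few as 202 + 202 − 288 = 116 time points, yet the formula divides by a single n that SAP 6.6.4 does not tie to the points present on both days.

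**The case against.** The sentence above the formula already specifies consecutive days, and no program or dataset specification is available to show that the formula would override it. That is fair: what can be shown is a contradiction, not a coding error.

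A reader might infer that MODD is inflated wherever days are missing. The documents do not support that. Missing days at either end of a session create no non-adjacent pair. With uncorrelated days the expected effect is nil, and with negative correlation it reverses. Randomly scattered gaps also tend to produce more non-adjacent pairs than a continuous outage does. One 7-day block lost inside 28 days leaves 21 valid days and 20 pairs, of which one is affected. At ρ = 0.5 its gap of 8 days gives R = √[(1 − 0.5^8)/0.5] = 1.411 and a session ratio of 1 + 0.411/20 = 1.021.

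A reader might also infer that dropping a whole visit creates pairs eight or more days apart. That follows only from the session wording in 6.6.4.2. If pairs stay within a visit, as 6.6.4 has it, a dropped visit creates no pair.

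Nor is bias between arms established. A shift common to both arms largely cancels, and the documents give no evidence that wear differs by arm. SAP 6.6.1 does derive daily time in range by day since the weekly dose for LY3209590, so a weekly pattern in one arm is conceivable. Protocol 2.2, however, describes the profile of weekly insulins as nearly flat. Protocol 8.1.1.2 manages wear, and SAP 4.4.2.1 summarises missing-data patterns by day, visit and session.

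What stands is the mismatch itself, which none of these points removes.

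**Conclusion.** The inconsistency is certain from the text: by the SAP's own notation, the formula includes pairs that its definition excludes. Its effect is conditional. It needs invalid days between valid ones. The expected bias is upward only if adjacent days are positively correlated and the correlation decays with the gap. Under assumed correlations of 0.2 to 0.7 it is about 1% or less for one isolated gap in 28 days, and about 4% to 13% for eight. Differential bias further requires gap patterns or correlation to differ by arm.

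The point is minor. MODD is one of several variability measures in SAP 6.6.4, beside within-day and between-day SD and CV and the glucose risk indices. The endpoint it serves is other secondary with no multiplicity control, so no primary or key secondary conclusion depends on it.

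**What to change.** In SAP 6.6.4.2, before unblinding:
- Sum only over pairs of valid CGM days on adjacent calendar dates, at time points observed or interpolated on both days.
- Divide by the number of such pairs instead of m-1, and within each pair by the number of shared time points instead of n.
- State whether pairs are formed within a visit or within a CGM session, and align the definitions of k and m in 6.6.4 with that choice.
- Set MODD to missing for a participant with no adjacent valid pair.

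The cost is a few lines of SAP text and, in the derivation program, a date condition and two changed divisors. Participants with gaps contribute fewer day pairs. Because three valid days need not be adjacent, an occasional participant will have no MODD value.

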6.7. Appendix 7: MedDRA PT for Diabetic Retinopathy or Maculopathy

The following PT will be used to identify TEAEs of diabetic retinopathy or maculopathy (see Section 4.6.2.1.7):

- Amaurosis
- Amaurosis fugax
- Arteriosclerotic retinopathy
- Blindness
- Blindness transient
- Blindness unilateral
- Choroidal neovascularisation
- Cystoid macular oedema
- Detachment of macular retinal pigment epithelium
- Detachment of retinal pigment epithelium
- Diabetic blindness
- Diabetic eye disease
- Diabetic retinal oedema

- Diabetic retinopathy
- Diabetic uveitis
- Diplopia
- Exudative retinopathy
- Eye laser surgery
- Fundoscopy
- Fundoscopy abnormal
- Intra-ocular injection
- Macular detachment
- Macular oedema
- Maculopathy
- Noninfective chorioretinitis
- Noninfective retinitis
- Phacotrabeculectomy
- Retinal aneurysm
- Retinal arteriovenous malformation
- Retinal artery embolism
- Retinal artery occlusion
- Retinal artery stenosis
- Retinal collateral vessels
- Retinal cryoablation
- Retinal detachment
- Retinal exudates
- Retinal haemorrhage
- Retinal laser coagulation
- Retinal neovascularisation
- Retinal oedema
- Retinal operation
- Retinal thickening
- Retinal vascular disorder
- Retinal vascular occlusion
- Retinal vein occlusion
- Retinitis
- Retinopathy
- Retinopathy haemorrhagic
- Retinopathy hypertensive
- Retinopathy hyperviscosity
- Retinopathy proliferative
- Scintillating scotoma
- Sudden visual loss
- Venous stasis retinopathy
- Vision blurred
- Visual acuity reduced
- Visual acuity reduced transiently
- Visual impairment
- Vitrectomy

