- Any clinically significant abnormal laboratory findings or other abnormal safety assessments that are associated with the underlying disease, unless judged by the investigator to be more severe than expected for the participant's condition.
- The disease or disorder being studied or expected progression, signs or symptoms of the disease or disorder being studied, unless more severe than expected for the participant's condition.
- Medical or surgical procedure (for example, endoscopy and appendectomy): the condition that leads to the procedure is the AE.
- Situations in which an untoward medical occurrence did not occur (social and/or convenience admission to a hospital).
- Anticipated day-to-day fluctuations of preexisting disease(s) or condition(s) present or detected at the start of the study that do not worsen.

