10.3.4. Recording and Follow-Up of AE and/or SAE and Product Complaints

AE, SAE, and Product Complaint Recording

• When an AE/SAE/product complaint occurs, it is the responsibility of the investigator to review all documentation (for example, hospital progress notes, laboratory reports, and diagnostics reports) related to the event.• The investigator will then record all relevant AE/SAE/product complaint information in the participant's medical records, in accordance with the investigator's normal clinical practice. AE/SAE information is reported on the appropriate CRF page and product complaint information is reported on the Product Complaint Form.
Note: An event may meet the definition of both a product complaint and an AE/SAE. In such cases, it should be reported as both a product complaint and as an AE/SAE.
• It is not acceptable for the investigator to send photocopies of the participant's medical records to Sponsor or designee in lieu of completion of the CRF page for AE/SAE and the Product Complaint Form for product complaints.• There may be instances when copies of medical records for certain cases are requested by Sponsor or designee. In this case, all participant identifiers, with the exception of the participant number, will be redacted on the copies of the medical records before submission to Sponsor or designee.• The investigator will attempt to establish a diagnosis of the event based on signs, symptoms, and/or other clinical information. Whenever possible, the diagnosis (not the individual signs/symptoms) will be documented as the AE/SAE.

Assessment of Intensity

The investigator will make an assessment of intensity for each AE and SAE reported during the study and assign it to one of the following categories:

- Mild: A type of adverse event that is usually transient and may require only minimal treatment or therapeutic intervention. The event does not generally interfere with usual activities of daily living.
- Moderate: A type of adverse event that is usually alleviated with additional specific therapeutic intervention. The event interferes with usual activities of daily living, causing discomfort but poses no significant or permanent risk of harm to the research participant.

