4.6.2. Adverse Events

Events that are newly reported after the first dose of investigational product (IP) or reported to worsen in severity from baseline will be considered treatment emergent adverse events (TEAEs). The Medical Dictionary for Regulatory Activities (MedDRA) lowest level term (LLT) will be used in the treatment-emergent assessment. The maximum severity for each LLT during the baseline period (see the table in Section 4.1) will be used as baseline severity.

The table below describes the analysis related to AEs.

Analysis	Details
Overview of AEs	
Number and percentage of participants who experienced:
 
 • SAE, • Death, • Discontinuation from study treatment due to an AE, • Discontinuation from study due to an AE, • TEAE, and • TEAE related to study treatment.
Summary by PT within SOC	
Number and percentage of participants with AEs using MedDRA PT nested within SOC:
 
 • TEAE, • Maximum Severity TEAEs, • SAE, and • AE leading to permanent discontinuation of study treatment. 
Events will be ordered by decreasing risk difference within SOC. SOCs will be listed by decreasing risk difference.
 
For each participant and TEAE, the maximum severity for the MedDRA PT is the maximum postbaseline severity observed from all associated LLTs mapping to the MedDRA PT. The maximum severity will be determined based on the non-missing severities.

Analysis	Details
Summary by PT (within SMQ when applicable)	
Number and percentage of participants with TEAEs using MedDRA PT (irrespective of SOC):
 
 • TEAEs occurring in $\geq 1\%$ before rounding in LY3209590 group, and • TEAE of safety topic of interest by PT (within SMQ when applicable). 
Events will be ordered by decreasing risk difference.

Listing	
Separate listings for the following AEs or events will be provided:
 
 • SAE including death; • AEs leading to study treatment discontinuation; • Severe hypoglycemia; • Events sent to the external adjudicator for MACE adjudication • Participants who receive rescue therapy due to severe/persistent hyperglycemia; • Persistent-recurrent hypoglycemia reported by investigators; • Persistent-recurrent hypoglycemia identified by programming; and • Medication errors of interest.

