4.6.2.1.7. Diabetic Retinopathy or Maculopathy

The diabetic retinopathy or maculopathy will be searched by MedDRA PTs from all TEAEs. The list of PTs for the search is provided in [Appendix 7](#) (Section 6.7). A summary of treatment-emergent retinopathy or maculopathy by PT will be provided.

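### The retinopathy search list includes Vitrectomy but no vitreous haemorrhage term, so a bleed reported only under that name may fall outside the topic summary

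*SAP*

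**What the plan says.** SAP 4.6.2.1.7 describes the search in one sentence: "The diabetic retinopathy or maculopathy will be searched by MedDRA PTs from all TEAEs". It refers to Appendix 7 for the terms and specifies the output: "A summary of treatment-emergent retinopathy or maculopathy by PT will be provided". It names no standardised MedDRA query and no case review. Systemic hypersensitivity (SAP 4.6.2.1.3), by contrast, has three such queries plus case review of notable events.

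Appendix 7 opens with "The following PT will be used to identify TEAEs of diabetic retinopathy or maculopathy" and then gives the PTs alphabetically, ending at *Vitrectomy*. Its two haemorrhage entries are *Retinal haemorrhage* and "Retinopathy haemorrhagic". It also has procedure and examination entries such as "Retinal laser coagulation".

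Two protocol rules govern what sites record. Section 10.3.1, in its list of what does not count as an AE, has "Medical or surgical procedure (for example, endoscopy and appendectomy): the condition that leads to the procedure is the AE". Section 10.3.4 adds: "Whenever possible, the diagnosis (not the individual signs/symptoms) will be documented as the AE/SAE".

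SAP 4.6.2 also plans a general tabulation covering all TEAEs: "Number and percentage of participants with AEs using MedDRA PT nested within SOC".

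**The concern.** The SAP's case definition and the protocol's recording rules do not meet for one event. The list can pick up a vitreous bleed treated surgically through the name of the operation, or through visual symptoms such as *Vision blurred* or *Sudden visual loss*. The protocol steers sites away from recording either of these when a diagnosis is available. The name it steers them towards, the bleed itself, is not listed.

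The list is otherwise broad. It takes in *Diplopia*, *Scintillating scotoma* and *Retinopathy hypertensive*, so the omission is hard to read as a choice for specificity.

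What is at stake is the completeness of one named safety topic. The schedule of activities has no eye examination, and the systems that Protocol 8.2.1 requires at minimum in the screening examination do not include the eye. Ascertainment therefore rests on reported AEs, and for this topic the PT list is the whole case definition.

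**Working it through.** No figure in the plan bears on this point, so there is none to reproduce. The check is a count of the list, followed by tracing how one event would be recorded.

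**Counts from SAP Appendix 7**

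- Terms listed: 59, all different.
- Terms that refer to the vitreous: 1, *Vitrectomy*, a procedure. Vitreous conditions: 0.
- Haemorrhage terms: 2, *Retinal haemorrhage* and *Retinopathy haemorrhagic*, both retinal.
- Procedures or examinations: 8 (*Eye laser surgery, Fundoscopy, Intra-ocular injection, Phacotrabeculectomy, Retinal cryoablation, Retinal laser coagulation, Retinal operation, Vitrectomy*). Share: 8 / 59 = 13.6%.
- Conditions, findings or symptoms: 59 − 8 = 51.

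**Tracing a vitreous bleed treated by vitrectomy**

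| What the site might report | Protocol direction | On the list? |
|---|---|---|
| The operation | Not the AE (10.3.1) | Yes, *Vitrectomy* |
| A visual symptom | Not where a diagnosis can be given (10.3.4) | Yes, several terms |
| The bleed | Consistent with both rules | No |
| The underlying retinal disease | Also consistent with both rules | Yes, e.g. *Retinopathy proliferative*, *Diabetic retinopathy* |

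The search fails when the third row is the only one used. The fourth row rescues the participant only if the listed diagnosis is itself treatment-emergent. Under SAP 4.6.2 that means newly reported after the first dose or worsened in severity from baseline. Retinopathy already present at baseline and not recorded as worsened would not be picked up.

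The gap is narrow. Conditions that could lead to laser treatment or intra-ocular injection, such as *Diabetic retinopathy* and *Macular oedema*, are listed as conditions, so the same rule does no harm there.

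**Where the bleed would still appear**

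- The PT-within-SOC table of all TEAEs (SAP 4.6.2).
- The listings, if the event is serious or leads to stopping study treatment (SAP 4.6.2).
- The table by PT irrespective of SOC only if the PT reaches 1% of the LY3209590 group before rounding. With 888 / 2 = 444 participants in that arm, 4 / 444 = 0.90% and 5 / 444 = 1.13%, so at least 5 participants would be needed.

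**After the fix:** 51 + 1 + 8 = 60 terms, and vitreous conditions go from 0 to 1. Sample size, power and alpha are unchanged.

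**The case against.** The strongest reply is that little is lost. Most of the list is conditions, findings or symptoms, and an extra procedure term costs no sensitivity. A site following Protocol 10.3.1 and 10.3.4 may well report the retinal disease, which is listed. The bleed remains in the general TEAE tables, and SAP 4.6 sets Fisher's exact test with a risk difference and confidence interval as the default comparison. SAP 4.6.2.1.7 promises only a summary by PT and writes out no combined any-term count, so the omission may remove one row without distorting the others. Retinopathy is not among the trial's objectives, nor among the potential risks in Protocol 2.3.1.

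All of this stands, and it sets the severity. It does not close the gap, because the topic summary is meant to gather these events in one place and one plausible name is absent.

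It is also fair to say that the list is alphabetical and stops exactly where vitreous haemorrhage would come next, so a lost last line would look the same. Nothing marks a gap, so the list is taken as complete. A glance at the SAP original would settle it.

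Three stronger readings are tempting but not supported:

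- A reader might infer that the search as a whole depends on procedure terms. It does not: 51 of 59 terms are something else.
- A reader might infer that every bleed leading to vitrectomy is missed. Only those with no listed treatment-emergent term for the same participant are, and nothing in the documents says that a bleed is the usual reason for vitrectomy.
- A reader might infer that a difference between arms would go unseen. It could be absent from this summary, but the PT-within-SOC table would still show it.

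**Conclusion.** The point holds as a minor gap in one descriptive safety summary. An event reported only as vitreous haemorrhage may be missed by the SAP 4.6.2.1.7 search, while remaining in the general TEAE tables. The undercount cannot be sized: the documents give neither an event rate nor the proportion of such bleeds that would be reported without a listed diagnosis.

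The conclusion rests on two assumptions. First, a reported vitreous haemorrhage codes to its own PT and not to a listed retinal term; the dictionary is not part of the documents. Second, such a bleed belongs within the topic. The documents do not say so directly, although the inclusion of *Vitrectomy* points that way. The finding does not depend on vitreous haemorrhage being common or being the main reason for surgery.

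**What to change.** Add the PT *Vitreous haemorrhage* to Appendix 7. State there that the procedure PTs are kept as supplementary terms only, because Protocol 10.3.1 directs sites to report the underlying condition.

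The cost is one search term and one sentence, with no new data collection. SAP 4.1 allows changes to analysis methods that do not alter a principal feature of the protocol to be described in the SAP or the clinical study report. If the database is already locked, provide the expanded search as a labelled supplementary summary beside the planned one.

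The downside is that a few vitreous bleeds of non-diabetic cause may be counted. They stay identifiable because the table is by PT.
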